Recruitment was conducted between the dates of the 1st of October and the 2nd of November, 2020. Participants in the intervention group commenced the education and hypnotic intervention on November 2nd, 2020. Participants were recruited directly online using the Pelvic Pain Foundation of Australia social media sites, and via health practitioners working with PPP, who provided study information to their clients. Participants who expressed an interest were contacted by email, and provided with the Participant Information Sheet and Consent Form. Once consent forms were received, participants were sent the questionnaires for the outcome measures.

Allocation

Participants were allocated to either the intervention or waitlist control groups. The intervention group received seven weeks of hypnotic intervention therapy in the form of audio recordings of hypnosis sessions provided online. The waitlist control group received no intervention.

Blinding

Blinding for participant or psychologist was not possible, as participants required notification of the time line for hypnotic intervention. A total number of 40 participants commenced the trial, with 20 allocated to the intervention group, and 20 allocated to a waitlist control. Participant details were placed into unlabelled, sealed, envelopes.

Randomization

Randomization was conducted using a basic randomization software template. Once group allocation was complete, participants were notified of their group

allocation. The waitlist control group received support for two months upon completion of the trial. Recruitment and contact with participants were undertaken by the primary researcher, whereas randomization was undertaken by an independent statistician.

Procedure

After allocation, participants in the intervention group were sent a link to provide them with access to the hypnosis recordings when the trial commenced. The information sheet and seven hypnosis recordings were accessible on a website for the study. The intervention also contained one session of education regarding PPP and hypnosis. Participants in the intervention group were instructed to read the health resources provided, that included information on the anatomy of the pelvis and the basics of pain education before commencing the hypnosis recordings. Intervention group participants then completed seven online hypnosis recordings, one per week for seven weeks.

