This study utilized a series of questionnaires at baseline and the conclusion of the pilot trial in line with the outcomes of interest. The outcome measures included the Generalised Anxiety Disorder Scale 7-item (GAD-7)³⁴, Patient-Health Questionnaire 9-item (PHQ-9)³⁵, 10-point Visual Analogue Scale measuring pain severity, Brief-COPE³⁶, Pain Catastrophizing Scale (PCS)³⁷, the Pain Disability Index (PDI)³⁸ and the Short Suggestibility Scale (SSS)³⁹. The questionnaires were converted to an online format using SurveyMonkey⁴⁰ software, then a link to the study website was emailed to participants. The questionnaires utilized are listed below.

Feedback on recording use and the study

The primary outcome was to establish the feasibility of the trial. Therefore, the intervention group was asked to provide weekly feedback on the recordings and study overall and at the end of the pilot trial. At baseline, we asked participants to give an overview of their experience with chronic pelvic pain in an open response dialogue box. Each week of the seven week trial, participants in the intervention group were asked how many times they listened to each recording and for their feedback. We also asked for feedback on the trial overall in an open dialogue box in the concluding measures.

Questionnaires for the outcome variables

Our primary outcomes of interest were anxiety and depression. The secondary outcomes of interest included perceived pain severity, life impact of pain, coping styles and pain catastrophizing. We identified our outcomes of interest from previous research on chronic pain, previous systematic reviews and a recent scoping review looking at predictors of mental health outcomes for women with CPP.¹¹⁻¹⁴

Generalised Anxiety

Generalised Anxiety was measured using the GAD-7³⁴ at baseline and trial conclusion. The GAD-7³⁴ is a 7-item self-administered scale with seven questions related to Generalised Anxiety Disorder symptoms according to the Diagnostic and Statistical Manual 5th Edition (DSM-V).⁴¹ Persons completing the GAD-7³⁴ are asked '*over the last two weeks, how often have you been bothered by the following problems*', before being presented with the seven questions about anxiety symptoms, such as '*feeling nervous, anxious or on edge*'. Each of the seven items has a four-point Likert response scale, with

responses ranging from 0 (not at all) to 3 (every day). Total scores range from 0 to 21, with a higher score representing greater anxiety.

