The results of the questionnaires in the online SurveyMonkey⁴⁰ format were converted to an SPSS data file. SPSS⁴³ was used to provide baseline descriptive statistics for the control and intervention groups. Independent sample t-tests were then conducted in order to establish participant results for the outcomes of interest pre and post intervention. The comparison of group differences over time was undertaken using linear mixed effects modelling with group, time and group time interaction. Group time interaction was included in the

model as the formal test for the efficacy of the intervention. Linear mixed effects modelling was conducted using Stata statistical software.⁴⁴ A second model including suggestibility was then undertaken. Results were considered statistically significant at $p < 0.05$.

Sample size justification

Power calculations for the study were carefully considered. Current recommendations for pilot RCT sample sizes vary significantly, as they are by definition investigative in nature and the standardized effect size is unknown. For a main trial planned with 90% power and two-sided 5% significance in mind, Whitehead et al.⁴⁵ recommend a minimum of 10 participants per study arm in the pilot trial.

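### The formal efficacy test is a change-score comparison; adjusting each scale for its own baseline would usually be more precise and needs no extra data

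*Combined protocol and SAP*

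**What the plan says.** The Statistical analyses section states: "The comparison of group differences over time was undertaken using linear mixed effects modelling with group, time and group time interaction". The interaction is put into the "model as the formal test for the efficacy of the intervention". The only covariate mentioned is a different scale: "A second model including suggestibility was then undertaken". The same section also plans independent-sample t-tests before and after the intervention, which are unadjusted. No analysis uses the baseline value of the outcome scale as a covariate. The section does not state a covariance structure, an estimation method or degrees of freedom.

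The Outcome measures section fixes the number of time points at two: "This study utilized a series of questionnaires at baseline and the conclusion of the pilot trial in line with the outcomes of interest". The Blinding section gives the size: "A total number of 40 participants commenced the trial, with 20 allocated to the intervention group, and 20 allocated to a waitlist control". On the timing of baseline measurement, the Recruitment section says only: "Once consent forms were received, participants were sent the questionnaires for the outcome measures".

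The purpose is described in two ways. Under Feedback on recording use and the study: "The primary outcome was to establish the feasibility of the trial". Under Questionnaires for the outcome variables: "Our primary outcomes of interest were anxiety and depression".

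**The concern.** With one baseline and one follow-up, and with group, time and their interaction all free, the interaction has no more information to work with than each person's change score. Subtracting the baseline amounts to assuming that a participant one point higher at baseline would be one point higher at follow-up. For self-reported symptom scales the true slope is often below 1. The change score then over-corrects and carries baseline noise into the comparison. ANCOVA estimates the slope instead, at the price of one degree of freedom.

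The second model does not repair this. Suggestibility is measured only at baseline. Entered as a main effect, it leaves the interaction estimate unchanged with complete data.

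What is at stake is the width of the interval around the efficacy estimate in a trial of 40 people. Bias is not at issue.

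**Working it through.** **Inputs.** From the documents: n = 20 per arm, two time points, and the interaction as the efficacy test. Not in the documents, so assumed over a range: the baseline-to-follow-up correlation ρ, the ratio k of follow-up SD to baseline SD, and dropout. The plan has no power figure to reproduce. Its minimum of 10 per arm is a cited rule for pilots.

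**Step 1: the interaction is the change-score contrast.** A random-intercept REML model with group, time and interaction was fitted to a simulated data set with 20 per arm. It gave an interaction of -0.4448 (SE 0.3048). The difference in mean change gave the same estimate and SE. Adding a suggestibility main effect altered neither.

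**Step 2: variances**, in units of the baseline variance.
- Planned test: (2/n)(1 + k² - 2ρk).
- ANCOVA: (2/n) k²(1 - ρ²)[1 + 1/(2n - 4)]. At n = 20 the bracket is 37/36, the cost of estimating the slope.
- Reduction = 1 - k²(1 - ρ²)(37/36)/(1 + k² - 2ρk).

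Example with k = 1, ρ = 0.5: 1 - 0.75 × 1.0278/1 = 0.229. With k = 1.25, ρ = 0.7: 1 - 1.5625 × 0.51 × 1.0278/0.8125 = -0.008.

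| ρ | k = 0.8 | k = 1 | k = 1.25 |
|---|---|---|---|
| 0.5 | 41.3% | 22.9% | 8.2% |
| 0.7 | 35.5% | 12.6% | -0.8% |
| 0.8 | 34.2% | 7.5% | -2.8% |

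At k = 1 the reduction is also 33.2% at ρ = 0.3, 17.8% at 0.6 and 2.4% at 0.9. Break-even is at ρ = 2/(37/36) - 1 = 0.946. The true slope is kρ, and the worst case for ANCOVA is kρ = 1, where the change score happens to be right. The loss is then 37/36 - 1 = 2.8%, which is the bound with complete data.

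**Step 3: simulation.** With 200,000 trials per correlation at k = 1, the reductions were 23.0%, 12.8% and 7.5% for ρ = 0.5, 0.7 and 0.8. With t references, both tests had size 0.048 to 0.052 in all 24 settings examined (k from 0.8 to 1.5). With scores rounded and bounded to 0-21 (mean 8 and SD 5 assumed), the reductions were 22.9% and 12.7% at underlying correlations of 0.5 and 0.7.

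**Step 4: interval width.** Mean 95% half-widths in baseline SDs at k = 1:
- ρ = 0.5: 0.636 to 0.559, 12% narrower.
- ρ = 0.7: 0.492 to 0.461, 6% narrower.
- ρ = 0.8: 0.402 to 0.387, 4% narrower.

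Expressed as sample size, ANCOVA with 20 per arm is worth the planned test with 20/0.771 = 26 per arm at ρ = 0.5, or 20/0.874 = 23 at ρ = 0.7.

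**Step 5: dropout.** Suppose 5 of 20 per arm miss follow-up completely at random (k = 1). The comparison is ANCOVA on those followed up against the planned model fitted to all data with unstructured covariance. The variances are 0.1044 against 0.1263 (17% lower) at ρ = 0.5, 0.0704 against 0.0773 (9%) at 0.7, and 0.0496 against 0.0523 (5%) at 0.8.

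**Step 6: the unstated reference distribution.** If the planned model were fitted by maximum likelihood with a normal reference, which is an assumption, its size would be P(|t₃₈| > 1.96√(38/40)) = 0.064.

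**The case against.** The planned analysis is conventional and valid, and nothing in the plan contradicts it. Feasibility is given as the primary outcome, the sample was not sized for this test, and no decision hangs on its p-value. A variance reduction also sounds larger than the 4% to 12% change in interval width that a reader would see. Even with equal SDs, the ANCOVA interval came out wider in about 15% of simulated trials at ρ = 0.7 and 27% at ρ = 0.8. With k = 1.5 there is almost nothing to gain: +1%, -3% and +2% at ρ = 0.5, 0.7 and 0.8. Every figure rests on assumed values. Finally, the text is in the past tense, so the analysis may already have been done.

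Most of this stands as a limit on the weight of the point. It does not remove it. The plan itself makes the interaction its formal efficacy test, and it also calls anxiety and depression primary outcomes of interest. The downside is bounded at about 3% of variance, while much of the plausible range shows a gain several times that. Nor does the mixed model's use of incomplete records rescue it, as Step 5 shows. If the data have been analysed, the change becomes a sensitivity analysis. Nothing suggests that baselines were completed after allocation, but the text does not rule it out.

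**Conclusion.** The point holds as an optional improvement; the plan is not in error. With randomisation and a t reference the planned test keeps its size and costs only precision. Under equal SDs, complete data and 20 per arm, ANCOVA lowers the variance by about 23%, 13% or 7.5% at correlations of 0.5, 0.7 or 0.8. The gain is about 34% to 41% if follow-up SDs are 0.8 of baseline. It runs from an 8% gain to a 3% loss if they are 1.25 times baseline. The direction is well supported when SDs are equal or shrink. The size in this trial cannot be known from the documents.

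**What to change.** For each scale, estimate the between-arm difference at trial conclusion by regressing the follow-up score on arm and that scale's baseline score, and report it with a t-based 95% confidence interval. First confirm from completion dates that baseline questionnaires were finished before participants learned their allocation.

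If participants who miss follow-up are to stay in the model, use a mixed model with a common baseline mean (no group main effect), fitted by REML with separate variances at each time and a small-sample correction such as Kenward-Roger. With values missing only at follow-up, its maximum likelihood estimate is the ANCOVA estimate, so it helps mainly if some baselines are missing. Avoid a random-intercept version of that model, because it forces equal variances. In simulation its type I error was 0.072 to 0.087 at k = 1.25 and 0.092 to 0.109 at k = 1.5. Whichever model is used, state the covariance structure, estimation method and degrees of freedom.

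The cost is one regression per scale, a few lines of SAP text and the date check. No new data are needed. The Procedure section says the methodology did not change after the trial began, so the change must be documented. The document is dated 20/11/2020, before the concluding measures in the week of 21 December 2020. If outcomes had not been analysed, this is a plan change; if they had, label it a sensitivity analysis.
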